9.2	Data reporting.....	42
9.3	Data monitoring	42
9.4	Clinical investigation report.....	42
9.5	Filling and archiving.....	43
10	Amendments to the Clinical Investigation Plan	44
11	Deviations from the Clinical Investigation Plan	44
12	Device accountability	45
13	Compliance	45
13.1	Insurance	46
13.2	Publication policy and confidentiality.....	46
14	Adverse events, adverse device effects and device deficiencies	47
14.1	Definitions.....	47
14.1.1	Adverse Event (AE)	47
14.1.2	Adverse Device Effect (ADE).....	47
14.1.3	Device Deficiency (DD).....	47
14.1.4	Serious Adverse Event (SAE).....	48
14.1.5	Serious Adverse Device Effects (SADE).....	48
14.1.6	Anticipated and Unanticipated Serious Adverse Device Effects (ASADE and USADE).....	48
14.2	Adverse event causality.....	48
14.3	Adverse events severity.....	49
14.4	Follow-up of Adverse Events	49
14.5	Expedited Reporting of Adverse Events	50
14.6	Anticipated adverse events.....	50
14.7	Timeline for reporting AE	51
15	Vulnerable and dependent population	51
16	Suspension or premature termination of the clinical investigation	51
17	Reference	53
18	Appendix	54
18.1	Quality of life questionnaire in Czech version	54
18.2	Spectacle independence questionnaire in Czech version	55

 PERFECT LENS	Clinical Investigation Plan	Page no.	7 z 55
		Version	02
PL-RIS01		Date	2023-07-18

2 Synopsis

Title of the investigation	Assessment of Clinical and Refractive Outcomes of the Use of a Femtosecond to Treat the Symptoms of Presbyopia in a Patient with an Implanted Mono focal IOL
Clinical Investigation plan number	PL-RIS01
Investigational device	Perfector
Sponsor	Perfect Lens LLC [name] [name]
No. of investigational site	Single center
Objective	The purpose of this research study is to evaluate the safety and efficacy of the treatment of the symptoms of presbyopia with a device (the "Device") in a patient with an implanted monofocal IOL. The Device employs a generic femtosecond laser used in numerous other ophthalmic procedures. The Device uses low levels of energy from the femtosecond laser (the "Treatment") to create near vision in both eyes for a patient with an implanted mono focal intraocular lens ("IOL").
Clinical investigation design	This is a prospective, single-center, single-arm study. The Treatment utilizes a femtosecond laser creating a near vision foci in the implanted mono focal intraocular lens. The study will treat both eyes of a patient to ensure that the patient has effective multi focal vision. The Treatment for both eyes may be on the same day, assuming there are no issues with the initial validation Treatment. The duration of the study is expected to be 4 months for each patient. In addition to preoperative and operative visits, 3 postoperative visits are planned: 1 week, 1 month and 3 months postoperatively. With an overall Treatment period of 1 month, the duration of the entire study is expected to be 6 months in total.
Population	Patients implanted with a mono focal IOL in both eyes
Inclusion and exclusion criteria	
Inclusion criteria:
 
 Ability to understand study requirements, follow study instructions and to return for required study follow-up visits as confirmed by provision of written informed consent;

 PERFECT LENS	Clinical Investigation Plan	Page no.	8 z 55
PL-RIS01		Version	02
		Date	2023-07-18

	
2. Subject has undergone cataract surgery and has had a monofocal lens implanted in both eyes;
 
3. Subject has no significant residual visual issues which the Investigator believes would make the patient ill suited for the Treatment;
 
4. Both eyes have CDVA vision of 20/25 or better at 4m.
 
Exclusion criteria:
 
 1. Subjects not able to complete the informed consent form; 2. Clinically significant corneal abnormalities including corneal dystrophy (e.g., epithelial, stromal, or endothelial dystrophy), inflammation, keratitis, keratoconjunctivitis, keratouveitis, keratopathy, keratectasia or edema per the Investigator's expert medical opinion; 3. Previous corneal surgery 4. Previous refractive surgery or proposed refractive surgery procedures throughout the entire duration of the subjects' participation in the clinical study (including, but not limited to LASIK, astigmatic keratotomy and limbal relaxing incisions); 5. History of or current retinal conditions or predisposition to retinal conditions including retinal detachment, diabetic retinopathy, age related macular degeneration which are assessed to by investigator to confound outcomes; 6. Amblyopia; 7. History of or current anterior or posterior segment inflammation of any etiology, or any disease producing an inflammatory reaction in the eye (e.g., iritis or uveitis); 8. Optic nerve atrophy; 9. Iris neovascularization; 10. Subjects with diagnosed degenerative eye disorders (e.g., macular degeneration or other retinal disorders); 11. Uncontrolled glaucoma; 12. Any subject currently participating in another investigational drug or device studies; and 13. Any subject disqualified by the Principal Investigator or Medical Monitor for any ocular issue.
Endpoints	Primary endpoints:

 PERFECT LENS	Clinical Investigation Plan	Page no.	9 z 55
PL-RIS01		Version	02
		Date	2023-07-18

	
There are three co-primary effectiveness endpoints at the 1-month post Treatment visit.
 
Distance Corrected Near Visual Acuity (DCNVA) at 40 cm. The hypothesis tested for is to demonstrate superiority of the near vision of treated IOL to the near vision provided by the pre-Treatment IOL.
 
Distance Corrected Intermediate Visual Acuity (DCIVA) at 66 cm. The hypothesis tested for is to demonstrate non-inferiority of the treated IOL to the pre-treated IOL (using a non-inferiority margin of 0.10 logMAR).
 
Best corrected distance visual acuity (CDVA) at 4m. The hypothesis tested is to demonstrate non-inferiority of the treated IOL to the pre-Treatment IOL for corrected distance vision (using a non-inferiority margin of 0.10 logMAR).
								
Other outcome measures	
The following is a list of additional outcomes measures:
 
Uncorrected and corrected distance visual acuity (UDVA)
 
Uncorrected and corrected intermediate visual acuity at 66 cm (UIVA)
 
Uncorrected near visual acuity at 40 cm (UNVA)
 
Corrected near visual acuity at 40 cm (CNVA)
 
Defocus curve
 
Contrast sensitivity
 
Subjective manifest refraction
 
Slit Lamp examination findings
 
Fundus examination findings
 
Intraocular pressure
 
Spectacle independence questionnaire
 
QoV patient questionnaire
 
Treatment satisfaction
 
Adverse Events
 
Device deficiency
								
Examination schedule	
 
 Preoperative	Day -60 to day -1	
 
 Surgery visit	Day 0	
 
 Postoperative 1 week	Days 5 to 9	
 
 Postoperative 1 month	Days 21 to 42	
 
	Preoperative	Day -60 to day -1	Surgery visit	Day 0	Postoperative 1 week	Days 5 to 9	Postoperative 1 month	Days 21 to 42
Preoperative	Day -60 to day -1								
Surgery visit	Day 0								
Postoperative 1 week	Days 5 to 9								
Postoperative 1 month	Days 21 to 42								

 PERFECT LENS	Clinical Investigation Plan	Page no.	10 z 55
		Version	02
PL-RIS01		Date	2023-07-18

	Postoperative 3 months	Days 70 to 98
Sample size	A total of up to 24 eyes from 12 patients will be enrolled in this clinical investigation.	
Statistical analyses	The study will use descriptive statistics to summarize quantitative and qualitative variables in the final report. For quantitative variables, it will provide measures such as mean, median, standard deviation, minimum, and maximum. For qualitative variables, it will present the number and percentage of patients in each category, including missing data.	

 PERFECT LENS PL-RIS01	Clinical Investigation Plan	Page no.	11 z 55
		Version	02
		Date	2023-07-18

3 Administrative structure

PRINCIPAL INVESTIGATORS: [name], PhD, FEBOS-CR
 Gemini Eye Clinic
 [name]
 Zlín, Czech Republic

DEVICE OPERATION: [name]
 Perfect Lens, LLC
 [name]
 [name]

[name]
 Perfect Lens, LLC
 [name]
 [name]

MEDICAL MONITOR: [name].
 [name]
 [name]

DATA MONITOR: [name]
 Perfect Lens, LLC
 [name]
 [name]

STUDY MONITOR: [name]
 [name]
 Zlín, Czech Republic

SPONSOR: [name]
 Perfect Lens LLC
 [name]
 [name]

CONFIDENTIAL

 PERFECT LENS PL-RIS01	Clinical Investigation Plan	Page no.	12 z 55
		Version	02
		Date	2023-07-18

4 Identification and description of the investigational device

4.1 Model/type and manufacturer

Model: Perfector

Manufacturer: Perfect Lens LLC
[name]
[name]

Classification as per MDR: Class IIb according to the European CE medical device classification (Regulation (EU) 2017/745)

4.2 Intended purpose, subject population and indications of the investigational device

4.2.1 Intended Purpose

The Device is intended to alter the refractive characteristics of an implanted IOL. The Device uses the energy from a femtosecond laser to break ester bonds within the IOL structure and create hydrophilic areas within the IOL. These hydrophilic areas incorporate water molecules into the molecular structure of the IOL and thus change the refractive characteristics of the IOL. In the present case the changed refractive characteristics gives the patient a second focal spot and affords the patient near vision.

4.2.2 Subject Population

Patients with an implanted mono focal IOL who do not exhibit any clinically significant conditions that would prevent them from benefits of multifocal IOL.

4.3 Description of the investigational device

4.3.1 Parts of the Device

The Perfector consists of (i) a femtosecond laser, (ii) a scanner capable of using light to capture two and three-dimensional images from within optical scattering media, (iii) a scanner (the "OCT"), which performs a non-invasive imaging test that uses light waves to take cross section pictures of the interior of the eye and is able to locate the implanted intraocular lens, (iv) an optical focusing system using lenses and mirrors, (v) an objective lens, (vi) a computer, (vii) a camera, (viii) proprietary software, which controls the relationship between the scanners, the laser and the focusing system, (ix) non-proprietary software produced by the manufacturers of the laser, 2D scanner, computer, and OCT, (x) patient attachment which attaches patient to system for Treatment, and (xi) a power supply, which includes an emergency power supply (the "UPS"). All components, except the proprietary software, are "off the shelf" items which are used in medical devices in the marketplace today. The Perfector is mounted upon a movable cart that measures 5 feet wide by 2½ feet deep, by 6 feet high. It is powered by a 220-240 VAC mains power supply.

 PERFECT LENS	Clinical Investigation Plan	Page no.	13 z 55
PL-RIS01		Version	02
		Date	2023-07-18

[figure not shown]

Figure 1 Scheme of the Perfector device

The Device alters the IOL by changing a thin disc in the interior of the IOL. It directs laser light to the IOL and alters the hydrophilicity of the treated area. By altering hydrophilicity of this treated area, the Device is able to create multi focality within the implanted lens. The exposure of the interior of the IOL to the femtosecond laser energy increases the hydrophilicity that is within the IOL by creating additional hydroxyl and acid groups. These acid and hydroxyl groups are hydrophilic and create a gradient which attracts water molecules. The addition of the water molecules changes the refractive properties of the IOL by reducing the refractive index of the treated area.

4.3.2 Use of the Device

The Device is used to alter the refractive qualities of an implanted IOL. In this case the goal is to creating near vision in a patient with an implanted mono-focal IOL. The science behind the change is explained above. The following is an image of the Device immediately before a Treatment

 PERFECT LENS	Clinical Investigation Plan	Page no.	14 z 55
PL-RIS01		Version	02
		Date	2023-07-18

[figure not shown]

Figure 2 Perfect Lens laser system Perfector

CONFIDENTIAL

 PERFECT LENS PL-RIS01	Clinical Investigation Plan	Page no.	15 z 55
		Version	02
		Date	2023-07-18

The actual process for treating an implanted IOL consists of the following steps:

- 1) The nurse or physician i) dilates the eye and ii) administers numbing drops to the eye of the patient which is to be treated;
- 2) Once the patient's eye is sufficiently dilated the patient is placed on a table directly beneath the patient attachment which is attached to the Device;
- 3) The operator then enters the patient data and the change which is to be made to the IOL into the computer which guides the Device. The computer directs the scanner to create the exact laser exposure necessary to make the required change in the IOL;
- 4) The nurse or physician applies the eye speculum.
- 5) The patient is asked to focus on a alignment light inside the system. The operator measures the required tilt adjustement and the target is moved to the correct position.
- 6) The operator lowers the patient attachment to the patient's eye aligning the IOL with the scanning beam of the laser;
- 7) The patient's eye is attached to the Device using vacuum suction. The sclera of the eye is attached to the patient attachment in a docking procedure using a sterilized patient attachment. In the docking procedure the operator does not apply suction until the IOL is correctly aligned to the laser beam;
- 8) The operator of the Device can see the implanted IOL on the computer screen using the OCT and confirms that the laser is focused on the center of the implanted IOL;
- 9) Once the laser is focused the operator initiates the Treatment
- 10) Once the Treatment is completed the vacuum suction is released and the patient will be assessed.
- 11) Since there is no cutting or ablating of the eye the patient has minimal sclera irritation and good vision in the treated eye immediately after the Treatment but might be sensitive to light with their dialated pupil ; and
- 12) The change in the hydrophilicity of the implanted IOL will take up to 24-48 hours, thus the patient will not have near vision for that period; however, the patient's existing vision will be unaffected.

The Perfector is operated by a technician who has been trained in the use of the Device. Each technician has created over 50 multifocal lenses from monofocals in the laboratory and is trained for the operation of the Device.

 PERFECT LENS PL-RIS01	Clinical Investigation Plan	Page no.	16 z 55
		Version	02
		Date	2023-07-18

5 Justification for the design of the clinical investigation

5.1 Background

Cataract surgery with intraocular lens (IOL) implantation is the most commonly performed surgical procedure in the world. The safety and effectiveness of modern-day cataract surgery are well described in the literature. In 2022, over 30 million procedures were performed worldwide.

The standard cataract surgery includes removal of the natural lens and replacement with an artificial lens; Intra-ocular lens (IOL). The surgeon chooses the power of the IOL to match the size of the eye. The target focal point is usually designed for far vision and thus all presbyopia patients require glasses for near vision.

Premium multifocal IOLs are designed to correct both distance and near vision. A patient who has a multifocal IOL has the advantage of spectacle independence. The multifocal lenses are expensive and require a patient to decide to choose this IOL before the surgery. Potential side effects include reduction of contrast sensitivity and visual disturbances such as halos and glares.

The Treatment, created by Perfector, uses a femtosecond laser to create a multifocal lens after the mono focal IOL lens has been implanted in an eye. This Treatment diverts light from the far vision foci, creating a near vision foci in addition to the far vision foci. The Treatment creates, in the IOL, a 60/40 light split with a newly created focal spot. The new focal spot gives the patient superior near vision. The diversion of the light to the new foci will diminish the patient's contrast sensitivity in low light situations but the patient will maintain equivalent far vision.

Femtosecond lasers have been used in ophthalmology since 2001 when they were introduced for the purposes of cutting corneal flaps in LASIK. The femtosecond laser was formally introduced into cataract surgery in 2009 to create corneal incisions. The use of the femtosecond laser to create corneal incisions, perform capsulotomies, and fragment existing cataracts (collectively the "Approved Femtosecond Methodologies") has received FDA and CE-Mark approval. Hundreds of thousands of patients undergo safe and effective femtosecond laser refractive and cataract Treatment every year.

5.1.1 Laser Energy

In the proposed study, Perfector intends to use, low-fluence, low-dose femtosecond laser energy at a fraction of the energy of used in capsulotomies. The chart of energy used is set forth below. The Treatment was used to make refractive changes to implanted lenses in a study in Panama. After an injury to a patient in the initial Treatment, the energy used in the Treatment has been reduced by over 90%. There was no adverse event in the last 12 patients treated with the lower energy levels. The energy used to create near vision in the implanted IO is less than the revised energy levels used to correct refractive errors in Panama. The energy used in this Study will less than the revised energy levels used in Panama, where there were no injuries.

The energy delivered in the Study is non-ablative – i.e., it does not cut eye tissue, but only modifies the refractive index of the implanted IOL. Unlike lens explantation or post-cataract

 PERFECT LENS PL-RIS01	Clinical Investigation Plan	Page no.	17 z 55
		Version	02
		Date	2023-07-18

refractive surgery (LASIK/PRK), low-fluence femto-laser adjustment will not expose the eye to the risks of endophthalmitis, infection and many of the anterior segment and corneal problems associated with these procedures.

The Company has conducted an extensive laser safety study which is included in the investigator's brochure. The laser safety study states that the lack of energy and location of the energy focus is not hazardous to the eye. It is important to note that the procedure does not target any ocular tissue.

5.1.2 Mechanism of Action

The Device alters the IOL by changing a thin disc in the interior of the IOL. It directs laser light to the IOL and alters the hydrophilicity of the treated area. By altering hydrophilicity of this treated area, the Device is able to create multi focality within the implanted lens. The exposure of the interior of the IOL to the femtosecond laser energy increases the hydrophilicity that is within the IOL by creating additional hydroxyl and acid groups. These acid and hydroxyl groups are hydrophilic and create a gradient which attracts water molecules. The addition of the water molecules changes the refractive properties of the IOL by reducing the refractive index of the treated area.^{2, 3, 4, 5, 6}

5.2 Pre-clinical testing

Summary of the preclinical testing that has been performed on the investigational device, together with an evaluation of the results of such testing, justifying its use in human subjects.

The index for all pre-clinical tests is attached as Exhibit B and is available for review. In summary:

The main preclinical material was the J&J material which is used during this study. The preclinical study literature is listing the J&J models (AAB00, ZCB00 or ZMB00). Additionally, the initial clinical study was performed on the same J&J material.

Study Name	Comment	Page # in Exhibit B	Material
Laser Safety Study	Optical hazard evaluation	1	NA
Exhaustive Extraction Study	No substantial differences between treated vs. untreated	43	J&J material
Leachable Study	No additional leachable created by the Treatment	53	J&J material

 PERFECT LENS PL-RIS01	Clinical Investigation Plan	Page no.	18 z 55
		Version	02
		Date	2023-07-18

Bubble Creation Study	Bubbles created during Treatment contained no cytotoxic species	114	J&J material
Photostability Study	Showed no effect on treated IOL	179	J&J material
Hydrolytic Study	Accelerated Aging Study showed Diopter Stability and no additional leachable	184	J&J material
Glistening Study	Optimized Treatment created no glistening	208	J&J material
Safety Sensor Test using Start Test installed in Device	Safety Sensors do identify problems in the Device	213	NA
Inorganic Soluble Study	Laser adjusted lens free of significant amounts of inorganic solubles within FDA standards	219	J&J material
YAG Study	YAG Treatment had no adverse effects on adjusted IOL	241	J&J material
Intramuscular implantation of treated IOL Study	No calcifications created	280	J&J material
Patient Attachment Study	Minimal cytotoxicity, sensitization and ocular irritation	326	NA
Physical Property Study	Treatment had no effect on physical properties of IOL	413	J&J material
Light Transmission Study	No significant reduction in light transmission	441	Zeiss hydrophobic material
Light Scattering Study	No significant increase in light scatter	446	Zeiss hydrophobic material

CONFIDENTIAL

 PERFECT LENS PL-RIS01	Clinical Investigation Plan	Page no.	19 z 55
		Version	02
		Date	2023-07-18

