7.6 Subjects

7.6.1 Inclusion and exclusion criteria

Inclusion criteria:

 1. Ability to understand study requirements, follow study instructions and to return for required study follow-up visits as confirmed by provision of written informed consent; 2. Subject has undergone cataract surgery and has had a mono focal lens implanted in both eyes; 3. Subject has no significant residual visual issues which the Investigator believes would make the patient ill suited for the Treatment; 4. Subject has in the treated eye of .5D or less; 5. Both eyes have UCDVA vision of 20/25 or better at 4m.
Exclusion criteria:

 1. Subjects not able to complete the informed consent form; 2. Clinically significant corneal abnormalities including corneal dystrophy (e.g., epithelial, stromal, or endothelial dystrophy), inflammation, keratitis, keratoconjunctivitis, keratouveitis, keratopathy, keratctasia or edema per the Investigator's expert medical opinion; 3. Previous corneal surgery 4. Previous refractive surgery or proposed refractive surgery procedures throughout

 PERFECT LENS PL-RIS01	Clinical Investigation Plan	Page no.	28 z 55
		Version	02
		Date	2023-07-18

the entire duration of the subjects' participation in the clinical study (including, but not limited to LASIK, astigmatic keratotomy and limbal relaxing incisions); 5. History of or current retinal conditions or predisposition to retinal conditions including retinal detachment, diabetic retinopathy, age related macular degeneration which are assessed to by investigator to confound outcomes; 6. Amblyopia; 7. History of or current anterior or posterior segment inflammation of any etiology, or any disease producing an inflammatory reaction in the eye (e.g., iritis or uveitis); 8. Optic nerve atrophy; 9. Iris neovascularization; 10. Subjects with diagnosed degenerative eye disorders (e.g., macular degeneration or other retinal disorders); 11. Uncontrolled glaucoma; 12. Any subject currently participating in another investigational drug or device studies; and 13. Any subject disqualified by the Principal Investigator or Medical Monitor for any ocular issue.

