7.8 Subject entry

Prior to enrolment in the clinical investigation, subjects from the standard post-operative cataract care population will be pre-screened via review of their medical charts to evaluate eligibility based on study inclusion/exclusion criteria. Study patients will be recruited from the Investigator's patient population, referrals, or IEC/IRB-approved recruitment materials.

The Informed Consent Process must be followed. Written informed consent for study participation is required prior to initiation of any study-specific procedure, and all subjects will be considered enrolled in the study upon their signature to the ICF.

 PERFECT LENS PL-RIS01	Clinical Investigation Plan	Page no.	29 z 55
		Version	02
		Date	2023-07-18

All enrolled subjects will be assigned a single unique subject identifier at the preoperative visit, and this identifier will be used throughout the clinical investigation.

An enrolment log will be maintained at each clinical site. This log will be provided to the investigational sites by the sponsor or designated CRO and will be stored in the Investigator's Site File. Current enrolment logs will be periodically provided to the sponsor or designated CRO as requested.

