7.9 Preoperative Visit - This visit will occur prior to enrolment (Visit 0)

Below is a list of study procedures to be done at Visit 0. All assessments must be documented in the source documentation and electronic case report form (eCRF), if applicable. Data from the Investigator's previous routine clinical evaluation (e.g., slit lamp exam) may be used, if the data 1) meets the requirements of this protocol, and 2) were collected within the -90 to -1 day pre-Treatment time period.

1. Review study specific inclusion/exclusion criteria (e.g., age, previous ocular history) to ensure that a potential subject meets all qualifications for participation in the study.
2. For a potential subject meeting all entry criteria via pre-screening, invite him/her to participate in the study, and carry out the informed consent process if he/she is interested.
3. Collect subject demographic, medical history information, and concomitant medication use.
4. Evaluate subject against all entry criteria. If the subject fails the criteria, the subject shall be eliminated from the study.
5. Determine current medication and medical history related to ophthalmic issues.
6. Perform the following test procedures on the eye to be treated. All measurements shall be done on a consistent basis for all test procedures.
 - a) Measure monocular and binocular uncorrected distance visual acuity (UDVA);
 - b) Measure monocular and binocular corrected distance visual acuity (CDVA)
 - c) Perform Manifest Refraction
 - d) Measure monocular and binocular uncorrected near vision acuity (UNVA) at 40 CM,
 - e) Measure monocular and binocular distance corrected near vision acuity (DCNVA),
 - f) Measure monocular and binocular uncorrected intermediate vision acuity (UIVA),
 - g) Measure monocular and binocular distance corrected intermediate vision acuity (DCIVA)
 - h) Measure CNVA at 40 cm

 Clinical Investigation Plan PL-RIS01	Page no.	30 z 55
	Version	02
	Date	2023-07-18

- i) Perform slit lamp biomicroscopy
- j) Perform fundus Exam
- k) Perform fundus and anterior segment OCT measurement
- l) Perform biometry measurements to determine Keratometry, Axial Length and ACD
- m) Perform tonometry to measure IOP
- n) Perform ITrace measurement
- o) Collect QoV patient questionnaire assessment for visual disturbances
- p) Collect spectacle independence questionnaire
- q) Collect a Defocus curve for patient's existing vision

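### Section 5.2 says the study uses the J&J lens material, but the eligibility criteria admit any monofocal IOL and no screening step checks lens material

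*Protocol*

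**What the plan says.** Protocol section 5.2 introduces its list of preclinical studies as the evidence that justifies using the device in people. On lens material it says "The main preclinical material was the J&J material which is used during this study". It adds that "the initial clinical study was performed on the same J&J material", and it names three J&J models from the preclinical literature. Both statements are given as fact.

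The passages that define the study population do not mention material:

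- Synopsis, population: "Patients implanted with a mono focal IOL in both eyes".
- Synopsis, inclusion criterion 2: "Subject has undergone cataract surgery and has had a monofocal lens implanted in both eyes".
- Section 4.2.2: "Patients with an implanted mono focal IOL who do not exhibit any clinically significant conditions".
- Section 7.6.1, inclusion criterion 2: "Subject has undergone cataract surgery and has had a mono focal lens implanted in both eyes".

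Screening applies those same criteria. Under section 7.8 candidates are "pre-screened via review of their medical charts to evaluate eligibility based on study inclusion/exclusion criteria", and the Visit 0 instruction in section 7.9 is "Evaluate subject against all entry criteria".

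**The concern.** The study does not supply the lens. It was implanted before enrolment, so eligibility is the natural place for the plan to fix the lens material, and it does not do so there. Section 5.2 and the eligibility criteria therefore describe different populations: recipients of J&J lenses in one, recipients of any monofocal lens in the other.

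The difference matters because of how the Treatment works. Sections 4.2.1 and 5.1.2 describe a laser-induced chemical change in the lens polymer: ester bonds are broken and new acid and hydroxyl groups form. Whether that change releases leachable substances, stays stable with ageing or is tolerated on implantation has to be shown for the material treated, and section 5.2 relies on tests of this kind. Two other sections lean on the same evidence. Section 6.2.3 calls the risk low partly because of the preclinical testing. Section 7.16 cites ageing studies in Exhibit B in its case for ending follow-up at 3 months.

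**Working it through.** The protocol gives no figure to reproduce on this point. The check is a count of the evidence in 5.2 by material, followed by a search for any rule that would confine enrolment to the material with that evidence.

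**Step 1. The table in section 5.2, by its Material column.**

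| Material | Studies | Number |
|---|---|---|
| J&J | extraction, leachable, bubble creation, photostability, hydrolytic (accelerated ageing), glistening, inorganic soluble, YAG, intramuscular implantation, physical property | 10 |
| Zeiss hydrophobic | light transmission, light scattering | 2 |
| Not applicable | laser safety, safety sensor, patient attachment | 3 |
| Any other lens material | none | 0 |

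Total: 10 + 2 + 3 = 15. Material-specific: 15 − 3 = 12. The J&J share is 10/12 = 83%, so calling it the main preclinical material is accurate. Every listed extraction, leachable, ageing and implantation test is on J&J material. The 2 Zeiss studies are optical only.

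**Step 2. Where lens material could be fixed or checked.**

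| Place | Items | Items naming lens material |
|---|---|---|
| Synopsis criteria | 4 inclusion + 13 exclusion = 17 | 0 |
| Section 7.6.1 criteria | 5 inclusion + 13 exclusion = 18 | 0 |
| Section 7.9, Visit 0 tests a to r | 18 | 0 |
| Section 7.17, examination matrix rows | 22 | 0 |
| Section 4.3.2, treatment steps | 12 | 0 |

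The two criteria lists carry the most weight, since that is where a restriction would belong. The other rows show that no later step makes up for its absence. Section 7.10 verifies the patient, the site and the side, but not the lens. Visit 0 biometry covers keratometry, axial length and anterior chamber depth.

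**Step 3. Could a general criterion do the work?** Inclusion criterion 3 concerns residual visual issues, and exclusion criterion 13 concerns any ocular issue. Both are discretionary, and neither addresses the composition of a well-functioning lens.

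**Step 4. Consequence.** A patient with another manufacturer's monofocal lens in both eyes, who meets the remaining criteria, passes chart review and Visit 0 and may be treated. This would breach no eligibility criterion, so it would not be recorded as an eligibility deviation under section 11. Section 7.8 also allows recruitment by referral, so the plan cannot assume that the site implanted the lens or chose its model.

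**The case against.** The case against giving this much weight has four parts.

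- *The 5.2 sentence is descriptive.* It does not say that only J&J lenses may be treated, and every J&J monofocal recipient meets criterion 2, so the two texts are not strictly incompatible. This is right as to form: 5.2 sets no explicit restriction. But it says which material the study uses and builds the justification on it, while the criteria do not secure that this will be so. If other materials are intended, the sentence is wrong and their supporting tests are not listed. One of the two texts needs an edit either way.
- *Screening would bring up the lens model.* Chart review and ocular history would probably show it, and confirming a monofocal lens in both eyes may well mean consulting the implant record. That is plausible, but the protocol does not ask for the material, and no criterion would act on it.
- *The sponsor operates the device at one centre with up to 12 patients.* The sponsor may in practice decline other lenses. This lowers the chance that the gap is ever used, but it is an unwritten safeguard.
- *Unseen documents may cover it.* Exhibit A (risk management), Exhibit B (the preclinical reports), Exhibit C and the investigator's brochure were not available, nor was part of section 5.3. They might hold tests on other materials or a lens-compatibility control. That limits what can be said about actual risk. It does not alter the eligibility criteria in the protocol.

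**Conclusion.** The concern holds. Section 5.2 says the study uses the J&J material, the eligibility text admits any monofocal IOL, and nothing in screening or treatment set-up checks the material. Following the criteria as written could expose an eye to a laser-induced polymer change in a material for which 5.2 lists no extraction, leachable, ageing or implantation test. Up to 24 eyes of 12 patients are to be enrolled, and the protocol gives no basis for estimating how many might carry another material.

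Confidence is high for the mismatch in the text. The safety consequence is stated only as a possibility. It rests on the 5.2 table as the available account of the preclinical evidence, and on no separate lens-compatibility control in the documents not seen. The issue should be resolved because it bears on the argument for exposing patients. It does not affect the planned analysis, which is descriptive.

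**What to change.** Reconcile section 5.2 with the synopsis, section 4.2.2 and section 7.6.1, in one of two ways.

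1. Carry the lens material stated in 5.2 into inclusion criterion 2, in both the synopsis and 7.6.1, align 4.2.2, and add a check of the implanted lens against the surgical record at chart pre-screening (7.8). The cost is one phrase and one chart check. The drawback is a possibly smaller recruitment pool.
2. If other materials are meant to be eligible, correct the sentence in 5.2 and cite the supporting material-specific tests for each lens material admitted. The cost is one corrected sentence and the references, provided that the tests exist.

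The choice between them, and which lenses are eligible, belongs to the sponsor and investigator.
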